4.1.4 Secondary Endpoints

The secondary endpoints of the study include the primary PK parameters and the treatment outcomes (per RECIST Version 1.1) as described below.

- Pharmacokinetic parameters, which include:
 - Maximum plasma concentration (C_{max})
 - Time to reach maximum concentration (T_{max})
 - Terminal half-life ($t_{1/2}$)
 - Area under the concentration-time curve in a selected time interval (AUC_{0-t})
 - Area under the concentration-time curve in the time interval from 0 to infinity ($AUC_{0-\infty}$)
 - Apparent clearance (CL/F)
 - Apparent volume of distribution (V_z/F)
 - Mean residence time (MRT)
 - Accumulation index based on AUC
- ORR
- DCR
- DoR
- PFS
- Percentage change in tumor size from baseline according to RECIST Version 1.1

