Prior to shipment, a PK sample requisition form (containing the details of each sample / label identification included in the shipment) will be prepared. All sample correspondence must contain the Study Number, Study Drug, and Site references (including emergency contact details and responsible shipment coordinator). All of the sample details on this log must correspond with the details included on the individual sample labels, as each sample label will be checked against the list by Centre Laboratories' sample coordination personnel. The log should be reviewed by the preparer and a second individual for accuracy and signed/dated by both individuals. (An example sample transfer sheet is used to document the general information regarding the shipment). To avoid sample mix-ups

or misidentification, the samples in the shipment will be sorted by patient number and sample time using segmented cartons.

Table 11 Pharmacokinetic Sampling Time Points

Visit Cycle and Day	Time Point
Cycle 1, Day 1	Pre-dose \leq 10 minutes
	Post-dose 1 hour (\pm 15 minutes)
	Post-dose 2 hours (\pm 15 minutes)
	Post-dose 4 hours (\pm 30 minutes)
	Post-dose 6 hours (\pm 60 minutes)
	Post-dose 8 hours (\pm 60 minutes)
Cycle 1, Day 2	Pre-dose \leq 10 minutes
Cycle 1, Day 15	Pre-dose \leq 10 minutes
	Post-dose 1 hour (\pm 15 minutes)
	Post-dose 2 hours (\pm 15 minutes)
	Post-dose 4 hours (\pm 30 minutes)
	Post-dose 6 hours (\pm 60 minutes)
	Post-dose 8 hours (\pm 60 minutes)
Cycle1, Day 16	Pre-dose \leq 10 minutes

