10 STATISTICAL ANALYSIS

All statistical analysis will be performed under the direction of Hutchison MediPharma personnel. Any data analysis carried out independently by the investigator should be submitted to Hutchison MediPharma prior to publication or presentation.

The final analysis will be based on patient data collected through study discontinuation or study termination. There is no planned formal interim analysis. However, the accrued data may be analyzed for internal decision-making purposes, for example to provide information for a potential Phase 3 study design.

Final analysis for each cohort will occur once the last patient had been followed for sufficient time for the analysis of primary endpoint. For instance, for Arm A, final analysis will occur when the last patient had been on treatment for at least 16 weeks or discontinued early following discontinuation criteria. Timing of final analyses for cohorts may be combined if they occur close together. Details of the statistical analysis and data reporting will be provided in the Statistical Analysis Plan (SAP) document finalized prior to database lock.

Data will be summarized using descriptive statistics (continuous data) and/or contingency tables (categorical data) for demographic and baseline characteristics, efficacy measurements, safety measurements, and PK measurements. Information regarding compliance with efficacy testing and availability of data will be documented. Graphical techniques (eg, waterfall plots, Kaplan-Meier curves) will be used when such methods are appropriate and informative. The baseline value used in each analysis will be the last (most recent) pre-treatment value. Time to event variables will be summarized descriptively using Kaplan-Meier medians and quartiles. Analyses will be based upon the observed data unless methods for handling missing data are specified. Analyses will be performed using SAS® (Version 9.1 or higher).

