10.5 Pharmacokinetic Analysis

All patients whose plasma samples are collected for analysis of the plasma surufatinib concentration and derivation of PK parameters will be included in the Pharmacokinetic Analysis Set (PKAS).

A non-compartmental model analysis will be performed for plasma concentration data by central lab using WinNonlin (enterprise version). The following statistic data will also be reported: mean value, standard deviation, median value, minimum value, maximum value, geometric mean value, and geometric mean coefficient of variation.

The individual and mean pharmacokinetic parameters determined following analysis of the surufatinib concentration versus time data, will include, but not be limited to total plasma exposure (AUC_{0-∞}), C_{max}, CL/F, and V_z/F. The t_{1/2} will also be estimated. Mean, standard deviation (SD) and coefficient of variation (CV) will be presented. The actual times of plasma sample collection will be used in the determination of the pharmacokinetic parameters.

The methods for calculating pharmacokinetic parameters of surufatinib:

- C_{max}: the maximum observed plasma concentration over the sampling period, taken directly from the data.
- T_{max}: time at which C_{max} occurred, taken directly from the data.
- K_{el}: the first-order rate constant associated with the negative slope of the terminal portion of the log-linear concentration-time curve. A minimum of three points will be used.
- Area under the plasma concentration versus time curve (AUC) to be determined by the linear trapezoidal rule, where AUC_{last} is the AUC from time zero until the last concentration point and AUC_{0-∞} is the AUC_{last} + last concentration point divided by K_{el}.
- Half-life (t_{1/2}) to be determined according to t_{1/2} = 0.693/K_{el} where possible.
- CL/F: systemic clearance to be determined according to Dose/AUC_∞
- V_z/F: apparent volume of distribution, determined according to CL/F/K_{el}
- Dose Proportionality: to be evaluated by investigating the linearity of the relationship between AUC and dose, and C_{max} and dose.
- Accumulation ratio: AUC_{Day15}/AUC_{Day1} or AUC_{Day29}/AUC_{Day1}

Where the concentration data are missing, or listed as less than Lower Limit of Quantification, they will be regarded as zero (0) if occurring before C_{max}. After C_{max}, zero points will not be included in calculations.

Individual and mean surufatinib concentrations will be plotted by dose level.

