2. INTRODUCTION

This document describes the rules and conventions to be used in the presentation and analysis of efficacy and safety data for Protocol 2015-012-00US1. It describes the data to be summarized and analyzed, including specifics of the statistical analyses to be performed.

This statistical analysis plan (SAP) is based on protocol version 7.0 (amendment 11) dated 19Mar2021.

The pharmacokinetics analysis plan will not be included in this document.

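### Protocol 10.5 sets missed concentrations before Cmax to zero, which lowers AUC and shifts the accumulation ratio whenever the missed value was truly positive

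*Protocol*

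**What the plan says.** Protocol 10.5 states one rule for two situations: "Where the concentration data are missing, or listed as less than Lower Limit of Quantification, they will be regarded as zero (0"). The rule covers samples taken ahead of Cmax. After Cmax the treatment reverses, and "zero points will not be included in calculations". AUC is "to be determined by the linear trapezoidal rule", and it feeds CL/F (dose divided by AUC to infinity), Vz/F, dose proportionality and the Day 15 to Day 1 accumulation ratio. Nothing restricts the zero rule to BLQ results, to the pre-dose sample or to Day 1.

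Table 11 (Protocol 8.4.2) samples at pre-dose, 1, 2, 4, 6 and 8 h on Days 1 and 15 of Cycle 1, with a further pre-dose sample the next morning.

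These quantities are declared endpoints. Protocol 4.1.4 lists AUC, CL/F and "Accumulation index based on AUC" for escalation. Protocol 4.2.4 lists AUC, CL/F, the accumulation ratio and dose proportionality for expansion.

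Two other statements matter. The opening of Protocol section 10 says "Analyses will be based upon the observed data unless methods for handling missing data are specified", so the sentence in 10.5 is a specified exception to an observed-data default. SAP section 2 says "The pharmacokinetics analysis plan will not be included in this document", and SAP 4.4, on changes from the protocol, lists only ECG additions.

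**The concern.** A BLQ value before the peak is a measurement known to lie between zero and a small limit, so zero is a conventional stand-in. A missed sample carries no such information. The 1-h and 2-h samples normally sit on the rising limb, and on Day 15 the pre-dose sample is a trough under repeated dosing. Zero is wrong for all of these.

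The error is one-sided. Every affected AUC moves down and every affected CL/F moves up, so errors across patients do not average out. The accumulation ratio can move either way, depending on which day has the gap. A reader of the PK results could not separate this from real differences in exposure.

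**Working it through.** The plan states no figure on this point, so there is none to reproduce.

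**Step 1: direction, from the protocol alone.** Under the linear trapezoidal rule, setting an interior point at time t(i) to zero removes C(t(i)) × [t(i+1) − t(i−1)]/2. With the Table 11 times (0, 1, 2, 4, 6, 8, 24 h):

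- 1 h: (2 − 0)/2 = 1.0 × C(1 h)
- 2 h: (4 − 1)/2 = 1.5 × C(2 h)
- 4 h, if the observed Cmax is later: (6 − 2)/2 = 2.0 × C(4 h)
- Day 15 pre-dose: (1 − 0)/2 = 0.5 × trough
- Day 1 pre-dose: 0.5 × 0 = 0

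Any positive concentration replaced by zero therefore lowers AUC. This needs no kinetic assumption.

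**Step 2: size, on assumed kinetics.** The documents give no human half-life, absorption rate or Tmax. The animal values in Protocol 2.2.2 are half-lives of 2.8–3.3 h and oral Tmax of about 3–4.5 h. The assumptions here are one-compartment oral kinetics, ka = 0.8/h, half-life 6–30 h, k = ln 2/half-life, and Day 15 at steady state. In units of F × dose/V:

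- Day 1: C(t) = [ka/(ka − k)] × [exp(−kt) − exp(−ka·t)]
- Day 15: the same, with each exponential divided by 1 − exp(−24k) or 1 − exp(−24ka) respectively

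**Worked case, half-life 12 h.** The Day 15 values at 0, 1, 2, 4, 6, 8, 24 h are 0.359, 0.872, 1.063, 1.097, 1.007, 0.904, 0.359, giving AUC0-24 = 17.86. Day 1 AUC0-24 is 13.03, with C(1 h) = 0.533 and C(2 h) = 0.743.

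- Day 15 2-h zeroed: 1.5 × 1.063 = 1.59; 1.59/17.86 = 8.9% lost.
- Day 15 2-h omitted: the 1–4 h area is 1.5 × (0.872 + 1.097) = 2.95 instead of 3.13; 0.17/17.86 = 1.0% lost (unrounded values).
- Day 15 1-h zeroed: 0.872/17.86 = 4.9% lost; omitted, 0.9%.
- Day 15 pre-dose zeroed: 0.5 × 0.359 = 0.18; 0.18/17.86 = 1.0% lost.

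Accumulation ratio:

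- True: 17.86/13.03 = 1.37.
- Day 1 2-h zeroed: 17.86/(13.03 − 1.5 × 0.743) = 17.86/11.91 = 1.50.
- Day 15 2-h zeroed: (17.86 − 1.59)/13.03 = 1.25.
- Both zeroed: 16.27/11.91 = 1.37, so the errors nearly cancel.

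**Across the assumed half-lives, Day 15 AUC0-24:**

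| Half-life | 2 h zeroed / omitted | 1 h zeroed / omitted | Pre-dose zeroed |
|---|---|---|---|
| 6 h | −11.9% / −1.8% | −6.2% / −1.8% | −0.4% |
| 8 h | −10.4% / −1.4% | −5.5% / −1.3% | −0.7% |
| 12 h | −8.9% / −1.0% | −4.9% / −0.9% | −1.0% |
| 30 h | −7.3% / −0.4% | −4.4% / −0.4% | −1.6% |

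At 6 h the 2-h sample is itself the highest sampled value. Once it is missed, the observed Cmax moves to 4 h and the rule applies to it.

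A wider grid (half-life 3–36 h, Tmax 2–5 h, both days) gives losses of 2.8–10.5% (1 h), 6.2–13.5% (2 h) and 9.7–15.9% (4 h, where the peak is no earlier).

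**Step 3: carry-over to CL/F.** CL/F uses AUC to infinity, so the AUC0-24 percentages do not transfer directly. At a 30-h half-life on Day 1, zeroing 2 h removes 1.5 × 0.775 = 1.16, which is 6.6% of AUC0-24 (17.70). Adding the tail, 0.591/0.0231 = 25.6, the loss is 1.16/43.3 = 2.7% of AUC to infinity. CL/F rises by 1/(1 − 0.027) − 1 = 2.8%.

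**Step 4: the Day 1 pre-dose sample.** If it is missed, zero is correct. Omitting it drops the 0–1 h trapezoid: 0.5 × 0.533/13.03 = 2.0% of Day 1 AUC0-24 at 12 h, and about 1.5–2.9% over 6–30 h. The correction must therefore exempt this sample.

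**The case against.** The strongest reply is that little depends on this. PK is secondary and Protocol 10.3 rules out formal hypothesis testing. The percentages apply per affected profile, and no missing-sample rate is given. If 5% of profiles (an assumption) lost one such sample at a 9% error each, the cohort mean would move by 0.05 × 9% = 0.45%. Medians and geometric means are also to be reported, and the median in particular is little moved by an isolated profile. A separate PK analysis plan exists, was not available for this review, and may already distinguish missing from BLQ. All of this stands, and it limits the severity. None of it makes zero the right value for a missed rising-limb sample or a Day 15 trough.

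A reader might also infer more than the documents support:

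- **That every missed early sample biases AUC.** It does not. The Day 1 pre-dose value is truly zero, and the rule reaches only samples before the observed Cmax.
- **That the ratio is always distorted.** The effect largely cancels when the same sample is missed on both days.
- **That the dose decision was affected.** Escalation reviews did consider PK data, but Protocol 5.1.1 and 5.1.2 tie the 30 November 2018 declaration of 300 mg QD to DLTs in 2 of 6 evaluable patients at 400 mg. Nothing links it to an AUC computed with zeroed samples.

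**Conclusion.** The point holds as a minor defect in a stated rule. The direction is certain from the trapezoidal formula: for any missed sample with a positive true concentration, AUC falls, CL/F rises, and the accumulation ratio goes up for a Day 1 gap or down for a Day 15 gap. The size is illustrative. On the assumed kinetics, an affected Day 15 profile loses about 7–12% of AUC0-24 for a zeroed 2-h sample, 4–6% for a 1-h sample and 0.4–1.6% for the pre-dose sample. These figures should not be read as cohort-level bias or applied unchanged to AUC to infinity or CL/F. Neither the protocol nor the SAP overrides the rule. Whether the separate PK analysis plan does is unknown.

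**What to change.** Amend the sentence in Protocol 10.5, and match it in the PK analysis plan, so that:

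1. BLQ values before Cmax stay at zero, on both days.
2. A missing Cycle 1 Day 1 pre-dose sample is also set to zero.
3. Every other missing sample is treated as missing and left out, so the trapezoid joins the neighbouring samples.
4. If the Day 15 pre-dose sample is missing, the Day 16 pre-dose value serves as the time-zero concentration (this assumes steady state); otherwise that AUC is not reported.

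The cost is a short change of text, and a few profiles may become non-evaluable. A small downward error remains for an omitted sample (about 0.4–2% in the illustration for 1 h or 2 h), because a straight line cuts under a concave rise. If the PK analysis plan already separates missing from BLQ, only the protocol sentence needs to be aligned with it.

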10.6 Tumor Assessment

Efficacy data will be summarized by dose group in the dose escalation phase and by disease cohort in the dose expansion phase. For the dose expansion phase, all summaries of efficacy data will be presented separately for the BTC, pNET, epNET, and STS arms.

The following efficacy endpoints will be analyzed:

10.6.1 Primary Efficacy Endpoints

- Patients with BTC: PFS rate at 16 weeks (according to RECIST Version 1.1);
- Patients with p-NET: PFS rate at 11 months (according to RECIST Version 1.1)
- Patients with epNET: PFS rate at 11 months (according to RECIST Version 1.1)
- Patients with STS: PFS rate at 4 months (according to RECIST Version 1.1).

PFS is defined as the time from the start date of study drug until the date of objective disease progression or death (by any cause in the absence of progression).

PFS will be described in tabular and graphical format using Kaplan-Meier method, including estimated median (in months) with 95% CI, 25th and 75th percentiles and Kaplan-Meier estimated probabilities with corresponding 80% and 95% CIs at several time points (including at least 16 weeks for BTC group and 11 months for pNET group). Censoring reasons will also be summarized.

10.6.2 Secondary Efficacy Endpoints

- ORR, defined as the proportion of patients with a best overall response of complete response (CR) and partial response (PR) per RECIST Version 1.1. To be assigned a status of PR or CR, changes in tumor measurements must be confirmed by repeat assessments performed no less than 4 weeks after the criteria for response are first met.
- DCR, defined as the proportion of patients with best overall response of CR, PR, or SD per RECIST Version 1.1.
- TTR, defined as the time between the start date of study drug until first documented response (CR or PR) according to RECIST Version 1.1.
- DoR, defined as the time from the first time that the objective response reaches CR or PR, whichever comes first, until the occurrence of PD or death (if the death of the patient occurs before recording the PD).
- Percent changes of tumor size from baseline of target lesion will be calculated at each visit, and the maximum percent per patient will be selected. Waterfall plots will be used to depict the tumor shrinkage in target lesion. These plots will display the best percentage change in target lesion size.

ORR and DCR will be estimated and 95% exact CIs based on the Clopper-Pearson method will be presented. The time to event endpoints, TTR and DoR will be described in tabular and graphical format using Kaplan-Meier method, including estimated median (in months) with 95% CI, 25th and 75th percentiles.

10.6.3 Exploratory Endpoints

- The values and changes from baseline in tumor markers will be summarized by tumor type (BTC, pNET, epNET, or STS) using descriptive statistics. Other exploratory analyses may be performed as appropriate.
- Overall survival is defined as the time interval between the start date of study drug and the date of death (any cause). The final known date of survival will be used as the censoring date for patients who have not been reported to have died by the time of analysis cut-off date. OS will be analyzed for only the BTC and STS cohorts based on the All Treated Population. OS will be described in tabular and graphical format using Kaplan-Meier method, including estimated median (in months) with 95% CI, 25th and 75th percentiles.

11 ETHICS

11.1 Good Clinical Practice

The study will be conducted in accordance with the protocol, ICH guidelines, applicable regulations and guidelines governing clinical study conduct, consensus and the ethical principles derived from international guidelines, including the following: Declaration of Helsinki and Council for International Organizations of Medical Sciences International Ethical Guidelines and Applicable ICH GCP Guidelines that have their origin in the Declaration of Helsinki.

11.2 Ethics Review

The Independent Ethics Committee (IEC)/Institutional Review Board (IRB) must review the protocol and amendments, IB, ICF, study-relevant materials (such as advertisements for patient recruitment), and any other essential documents. IEC/IRB approval is to be obtained prior to the start of the study at the site.

All amendments are to be reviewed and approved by the IEC/IRB and applicable regulatory authorities (as required) and documented. All SAEs and other significant safety findings should be reported to the sponsor, the IEC/IRB, and applicable regulatory authorities as required. During the study, protocol deviations that may increase a patient's risk should be reported to the IEC/IRB in a timely manner.

Protocols and any substantial amendments to the protocol will require health authority approval prior to initiation, except for changes necessary to eliminate an immediate hazard to study subjects.

The investigator will be responsible for the following:

- Providing written summaries of the status of the study to the IRB/IEC annually or more frequently in accordance with the requirements, policies, and procedures established by the IRB/IEC
- Notifying the IRB/IEC of SAEs or other significant safety findings as required by IRB/IEC procedures
- Providing oversight of the conduct of the study at the site and adherence to requirements of 21 Code of Federal Regulations (CFR), ICH guidelines, the IRB/IEC, European regulation 536/2014 for clinical studies (if applicable), European Medical Device Regulation 2017/745 for clinical device research (if applicable), and all other applicable local regulations

11.3 Patient Informed Consent

- Investigators or designees must obtain the signed ICF from patients prior to conducting any study-related procedures.
- The investigator or his/her representative will explain the nature of the study to the participant or to their legally authorized representative and answer all questions regarding the study.
- Participants must be informed that their participation is voluntary. Participants or their legally authorized representative will be required to sign a statement of informed consent that meets the requirements of 21 CFR 50, local regulations, ICH guidelines, Health Insurance Portability and Accountability Act requirements, where applicable, and the IRB/IEC or study center.

- Patients must be informed that they may withdraw consent to participate in the study without any limitations. If the patient cannot sign the ICF, a legally authorized representative of the patient must sign the ICF.
- If the patient and the legally acceptable representative are not able to read and write, an impartial witness should be present throughout the whole process of providing informed consent. Once the patient and the legally acceptable representative give their oral consent, the ICF should be signed by the impartial witness to confirm that the patient and the legally acceptable representative fully understand the study and their right to withdraw informed consent without any limitations.
- Informed consent should be recorded on the electronic case report form (eCRF).
- If the risk/benefit assessment changes after the safety analysis, the ICF needs to be reviewed and updated, and all updated information should be provided to patients (including patients who have already received the study drug).

11.4 Data Privacy

All information about the study drug (such as patent application, formulation, manufacturing process, and basic study information) is considered confidential as long as it is unpublished.

All information obtained in the study is considered confidential. The sponsor will open the information to investigational personnel and any other regulatory authority, when necessary. To ensure the completeness of the study analysis data, investigational personnel are accountable for providing all results and data to the sponsor.

Investigators must guarantee the privacy of patients by not disclosing patient-related information to third parties without authorization. Electronic case report forms and other documents submitted to the sponsor should not contain the patient's name.

- Participants will be assigned a unique identifier by the sponsor. Any participant records or datasets that are transferred to the sponsor will contain the identifier only; participant names or any information that would make the participant identifiable will not be transferred.
- Patients are identified only by the unique identifier. Investigators may retain the identification forms, which include patient numbers, names, and addresses. ICFs and other documents should be documented properly, and should not be given to the sponsor.
- The participant must be informed that his/her personal study-related data will be used by the sponsor in accordance with local data protection law. The level of disclosure must also be explained to the participant who will be required to give consent for their data to be used as described in the informed consent.
- The participant must be informed that his/her medical records may be examined by Clinical Quality Assurance auditors or other authorized personnel appointed by the sponsor, by appropriate IRB/IEC members, and by inspectors from regulatory authorities.

